3 STUDY DESIGN

3.1 Type of study

This is a cross-sectional, non-interventional, national (France), multicentre study, conducted on a population of 300 patients with GCA, to describe GCA management and patient characteristics

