3.2 Study plan

The study will be conducted in accordance with the professional code of ethics and the good epidemiological practice guidelines developed by the Association of French-Speaking Epidemiologists) and the STROBE (STrengthening the Reporting of OBservational studies in Epidemiology) recommendations for the drafting of reports and publications related to the study.

The information will be collected during a single visit to the internist or rheumatologist as part of the usual management of the patient with GCA. This study does not require any additional specific examination. Data will be collected from the medical file and from patient questionnaires on health status (SF-36 [36-Item Short Form Survey Instrument], EQ5D [EuroQol-5 Dimensions] and fatigue [FACIT-fatigue]. In addition, GCA activity will be evaluated using a global arteritis activity Visual Analog Scale (VAS) to be completed by the patient and the physician.

[figure not shown]

Figure 1 : Study design

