3.5.1.1 Inclusion criteria

Patients must meet the following criteria to be included in the study:

- At least 50 years old.
- Suffering from GCA as per investigator judgement, newly diagnosed or not.
- Starting or under treatment for GCA.
- Informed verbally and in writing about this study and not objecting to their data being electronically processed or subjected to data quality control.

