5.5.2 Description of GCA characteristics

First the following parameters will be presented:

- Time between diagnosis and inclusion will be described as quantitative variable (months) ([APPENDIX](#))
- Type of patient
 - Proportion of incident patients (newly diagnosed): patients with a diagnosis of GCA \leq 6 weeks from inclusion
 - Proportion of prevalent patients (not newly diagnosed): patients with a diagnosis of GCA $>$ 6 weeks from inclusion.

Then the following endpoints will be described overall and by type of patient (prevalent/incident), by type of diagnosis (time between the first medical events related to GCA and diagnosis to GCA as qualitative variable in 3 classes early/in standard time/late diagnosis), and by type of physicians who follows the patient.

- Initial presentation:
 - Proportion of patients with at least one cranial manifestation at diagnosis and the proportion of each symptom of this family (Headaches/ Scalp sensitivity / Anomalies of the temporal arteries (temporal artery sensitivity or decreased pulsation) / Ischemia-related vision impairment and-or loss / Mouth pain or jaw claudication during mastication / Stroke or transient ischemic attack (TIA) / Other)

Listing of Ischemia-related vision impairment / loss and other cranial manifestation at diagnosis will be presented.

- Proportion of patients with at least one PMR symptom at diagnosis and the proportion of each symptom of this family (Morning stiffness and-or pain in the shoulder girdle/ Morning stiffness and-or pains in the pelvic girdle/ Inflammatory arthromyalgia/ Peripheral arthritis/ Other)

A listing of other PMR symptom will be presented.

- Proportion of patients with at least one extracranial event (excluding PMR) at diagnosis and the proportion of each symptom of this family (Thoracic or abdominal aortic aneurysm and-or dilatation/ Aortitis and-or involvement of aortic branch(s) in imaging/ Angina and-or Myocardial infraction/ Claudication of an upper limb and-or claudication of a lower limb/ Sign of subclavian stenosis (asymmetry of pulse, blood pressure, subclavian murmur)/ Other)

A listing of other extracranial events (excluding PMR) will be presented.

- Value of ESR (mm/1st h) and CRP (mg/L) at diagnosis and at inclusion.
- Proportion of patients having abnormal value of ESR (ESR $>$ 50 mm/h)/CRP (CRP $>$ 25 mg/L) at diagnosis
- Proportion of patients having abnormal value of ESR (ESR $>$ 50 mm/h)/CRP CRP $>$ 25 mg/L) at inclusion

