- Proportion of patients with at least one general sign at diagnosis and the proportion of each sign (fever $>$ 38°C with no other etiology than GCA, weight loss and its value (%), alteration of the general condition)

For the value of ESR and CRP at diagnosis, only value measured in the previous month, the current month and the month following the date of diagnosis will be considered. For values at inclusion, only measures done within 6 month before the date of inclusion will be considered.

A listing of other initial characteristics related to GCA at diagnosis will be presented.

- Clinical form:
 - Proportion of patients with at least one relapse
 - In patient with at least one relapse:
 - Number of relapses per patient
 - Time between first relapse and diagnosis (months) ([APPENDIX](#))
 - Mean time between 2 consecutive relapses (months) ([APPENDIX](#))
 - The following information will be summarized by relapse:
 - Proportion of used criteria to assess relapse (Clinical/ Biological/ Imagery/ Other)
 - Proportion of patients using GCs just before the relapse
 - GCs dose at relapse diagnosis (mg/day)
 - Proportion of relapses of patients with Immunosuppressants just before the relapse
 - Proportion of relapses of patients with Targeted biologic therapy just before the relapse
 - Proportion of relapses of patients using other treatments just before the relapse
 - Proportion of relapses for which Glucocorticoids (GCs) were used as medical care for the relapse
 - GCs dose used for relapse medical care (mg/day)
 - Proportion of relapses for which Immunosuppressants were used as medical care for the relapse
 - Proportion of relapses for which Targeted biologic were used as medical care for relapse
 - Proportion of relapses for which other GCA (HORTON) treatments were used as medical care for relapse.
 - Distribution of GCs dependence
 - Current dose at inclusion (mg/day)
 - Number of kinetics per patient since diagnosis
 - Time between first kinetic and diagnosis (months) ([APPENDIX](#))
 - Proportion of patients with at least one kinetic ongoing at inclusion
 - Mean time between 2 consecutive kinetics (months) ([APPENDIX](#))
 - Total cumulative GCs dose according to investigator (excluding IV bolus) since diagnosis (mg) ([APPENDIX](#))
 - The following information will be summarized by Kinetic:
 - Kinetic duration (months) ([APPENDIX](#))
 - Proportion of kinetics with IV initial administration (bolus) (Yes/No)
 - If yes, total number of days

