8 STATISTICAL APPENDICES

APPENDIX (Derived data)

The following derived data will be calculated and included in the listings:

(1) **Enrollment duration**

Enrollment duration (days) = date of inclusion of the last patient – date of inclusion of the first patient

(2) **Time between first medical events related to GCA and diagnosis**

For prevalent patients (not newly diagnosed):

Time between first medical events related to GCA and diagnosis (months) = date of diagnosis – date of first medical events related to GCA

For incident patient (newly diagnosed):

Time between first medical events related to GCA and diagnosis (months) = date of diagnosis (in MM/YY format) – date of first medical events related to GCA

The date of diagnosis which is in format (DD/MM/YYYY) will be transformed into (MM/YYYY)

(3) **Time between diagnosis and inclusion**

For prevalent patients:

Time between diagnosis and inclusion (months) = (date of inclusion – date of diagnosis)/30.4375

If the date of diagnosis in format (DD/MM/YYYY) is not completed, the diagnosis date in format (MM/YYYY) will be used and the inclusion date will be transformed into (MM/YYYY).

For incident patients:

Time between diagnosis and inclusion (months) = (date of inclusion – date of diagnosis)/30.4375

The date of diagnosis in format (DD/MM/YYYY) will be used.

(4) **Duration of treatment taken**

Duration of treatment taken (months) = End date – start date +1

if ongoing treatment at inclusion:

Duration of treatment taken = Date of inclusion – start date +1

For this calculation, the date of inclusion which is in format (DD/MM/YYYY) will be transformed into (MM/YYYY) as the start date of treatment.

(5) **Time between first relapse and diagnosis**

Time between first relapse and diagnosis (months) = date of first relapse after diagnosis – date of diagnosis.

For this calculation, the date of diagnosis (for incident patient) which is in format (DD/MM/YYYY) will be transformed into (MM/YYYY) as the date of relapse.

(6) Mean time between 2 consecutive relapses

Time between 2 consecutive relapses (months) = [date of relapse (i+1) – date of relapse (i)]/(Total number of relapses per patient-1)

(7) Time between first kinetic and diagnosis

Time between first kinetic and diagnosis (months) = date of initiation of first kinetic – date of diagnosis

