Patient ID	Type of patient	Type of diagnosis	Physician who follows the patient	Specification of other initial characteristics related to GCA

STUDY : CHUGAI-ARTEMIS - Edition date: DDMMYY
Pgm : EFFICACYGCA.SAS

Table 16 - Efficacy analysis – Clinical Form - Number of relapses and time between relapses and diagnosis per patient - Analysis population (N=XX)

Parameter	Statistics	Total (N=XX)
Patient with at least one relapse		
No	n(%)	
Yes	n(%)	
	Filled, n(%)	
	Missing, n(%)	
In patients with at least one relapse		
Number of relapses per patient	Mean SD Median [Q1 ; Q3] [Min ; Max] Filled, n(%) Missing, n(%)	
Time between first relapse and diagnosis (months)	Mean SD Median [Q1 ; Q3] [Min ; Max] Filled, n(%) Missing, n(%)	
Mean time between 2 consecutive relapses (months)	Mean SD Median [Q1 ; Q3] [Min ; Max] Filled, n(%) Missing, n(%)	

The percentages are calculated compared to filled data
STUDY : CHUGAI-ARTEMIS - Edition date: DDMMYY
Pgm : EFFICACYGCA.SAS

Table 17 - Efficacy analysis – Clinical Form - Description of relapses - Analysis population (N=XX)

Parameter	Statistics	Total (N=XX relapses)
Used criteria to assess relapse* Clinical Biological Imagery Other	n(%) n(%) n(%) n(%) Filled, n(%) Missing, n(%)	
Patient using GCs therapy just before relapse No Yes	n(%) n(%) Filled, n(%) Missing, n(%)	
GCs dose at relapse (mg/day)	Mean SD Median [Q1 ; Q3] [Min ; Max] Filled, n(%) Missing, n(%)	
Patients with immunosuppressants just before the relapse No Yes	n(%) n(%) Filled, n(%) Missing, n(%)	
Patients with targeted biologic therapy just before the relapse No Yes	n(%) n(%) Filled, n(%) Missing, n(%)	
Patients using other treatments just before the relapse No Yes	n(%) n(%) Filled, n(%) Missing, n(%)	
Relapse for which GCs were used for the medical care of relapse No Yes	n(%) n(%) Filled, n(%) Missing, n(%)	
GCs dose used (mg/day)	Mean SD Median [Q1 ; Q3] [Min ; Max] Filled, n(%) Missing, n(%)	
Relapse for which immunosuppressants were used for the medical care of relapse No Yes	n(%) n(%) Filled, n(%) Missing, n(%)	
Relapse for which targeted biologic therapy was used for the medical care of relapse No Yes	n(%) n(%) Filled, n(%) Missing, n(%)	
Relapse for which other GCA (Horton) treatments were used for the medical care of relapse		

Table 17 - Efficacy analysis – Clinical Form - Description of relapses - Analysis population (N=XX)

Parameter	Statistics	Total (N=XX relapses)
No	n(%)	
Yes	n(%) Filled, n(%) Missing, n(%)	

* Multiple responses possible

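### Time to first relapse is summarised only in patients who relapsed before the single visit, so it is biased short by an unknown amount, and the relapse proportion has no time frame

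*SAP*

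**What the plan says.** SAP 3.1 describes the design: "This is a cross-sectional, non-interventional, national (France), multicentre study, conducted on a population of 300 patients with GCA". SAP 3.2 adds that "The information will be collected during a single visit to the internist or rheumatologist", so observation of every patient stops at that visit. Entry is open to anyone "Suffering from GCA as per investigator judgement, newly diagnosed or not" (SAP 3.5.1.1), provided the patient is "Starting or under treatment for GCA".

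Under clinical form, SAP 5.5.2 plans the proportion of patients with at least one relapse and then, within relapsers, "Time between first relapse and diagnosis (months"). The Table 16 shell in SAP 9.3.2 puts this under "In patients with at least one relapse", with mean, SD, median, quartiles and range. Appendix item (5) is a date difference: "Time between first relapse and diagnosis (months) = date of first relapse after diagnosis", minus the date of diagnosis. No censoring at inclusion, person-time rate or fixed-horizon proportion is planned.

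Two provisions bear on the point. SAP 5.5.2 says "Then the following endpoints will be described overall and by type of patient (prevalent/incident"), with a cut-off at 6 weeks, and also by timeliness of diagnosis and by type of following physician. Table 14 reports time from diagnosis to inclusion, but separately from relapse.

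**The concern.** A patient seen two months after diagnosis can only show a relapse within two months; a patient seen five years after can show one at any time up to five years. If only relapses already observed are kept, late relapses are lost selectively and the time is pulled downwards. For the same reason, a crude relapse proportion over patients observed for days to years is not a risk over any stated period.

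The 6-week split does not repair this. The prevalent group runs from just over 6 weeks to any number of years, and the incident group is cut off at 6 weeks.

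Clinical form is part of a named secondary objective. SAP 5.5.2 compares it by physician type, and Protocol 9.1.2 commits to comparing disease characteristics with the literature. In both comparisons, a difference in time since diagnosis alone could look like a difference in relapse.

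**Working it through.** **Nothing to reproduce.** The documents give no relapse rate, no time to relapse and no distribution of disease duration. Protocol 7.1.1 gives no sample-size rationale. Apart from step 1, the figures below therefore rest on assumptions.

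**1. Incident column (no assumption).** Incident means diagnosed at most 6 weeks (42 days) before inclusion, so an observed first relapse falls within 42 days of diagnosis. Appendix (5) works in calendar months. Diagnosis on 31 August with relapse on 12 October (42 days) counts as 2 months, so the recorded value can only be 0, 1 or 2, whatever the course of the disease.

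**2. Relapse proportion against duration.** With a constant hazard and true median m, the proportion relapsed by d months is 1 − 0.5^(d/m). For m = 24:
- d = 1.4 (6 weeks): 4%
- d = 12: 29%
- d = 24: 50%
- d = 60: 82%

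The disease is the same in all four cases; only time since diagnosis differs.

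**3. Truncation alone.** First relapse is exponential. Duration at the visit is gamma and independent of relapse. Two durations use proxies from the claims-database results in Protocol section 1: first glucocorticoid sequence 17.2 (SD 16.5) months, and follow-up 3.7 (SD 2.6) years, i.e. 44.4 (31.2) months. The middle one, 30 (25), is a pure assumption. Planned median in months, with its ratio to the true median:

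| True median | Duration 17.2/16.5 | Duration 30/25 | Duration 44.4/31.2 |
|---|---|---|---|
| 6 | 4.0 (0.67) | 4.8 (0.81) | 5.4 (0.90) |
| 12 | 6.0 (0.50) | 7.8 (0.65) | 9.2 (0.77) |
| 24 | 7.9 (0.33) | 11.0 (0.46) | 13.8 (0.57) |
| 36 | 8.8 (0.24) | 12.8 (0.36) | 16.4 (0.46) |

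If only half of patients ever relapse, the planned medians are essentially unchanged.

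**4. Adding the on-treatment criterion.** Time since diagnosis is uniform over 0–120 months. A patient is sampled only during the initial course or a course restarted by the first relapse, with mean course 18 or 24 months. Planned medians:
- true 12: 10.9 and 11.0 (ratios 0.91, 0.92)
- true 24: 20.7 and 20.3 (0.86, 0.85)
- true 36: 28.5 and 27.4 (0.79, 0.76)

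The time is still short, but much less so. The crude proportion moves the other way: for true median 36 it is 53–54%, at mean sampled durations of 29.5–32.7 months. Step 3 gives 38.5% for mean duration 30 without treatment selection. Relapse keeps patients on treatment and so eligible.

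**5. What a censored estimate can deliver.** Under step 3, Kaplan-Meier censored at inclusion targets the truth. Under step 4 with true median 24, the true 6-month risk is 1 − 0.5^(6/24) = 15.9%. Kaplan-Meier in patients diagnosed at most 12 months earlier gave 16.6–17.5%. The all-patient curve was off: its median was about 26.5 to 28 months against 24. Under a different treatment model (courses of about 16 months, extended after relapse), its 10-month risk was 30.3% against a true 25.1%, so the error can go either way.

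The recent subset cannot support a 12-month figure. For 300 patients, exponential durations of mean 24 months and true median relapse 24 months:
- subset size: 300 × (1 − e^(−12/24)) = 118
- at risk at 6 months: 300 × (e^(−6/24) − e^(−12/24)) × 0.5^(6/24) = 300 × 0.1723 × 0.8409 ≈ 43
- at risk at 10 months: 300 × (e^(−10/24) − e^(−12/24)) × 0.5^(10/24) = 300 × 0.0527 × 0.7492 ≈ 12
- beyond 12 months: none, by construction

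With treatment selection modelled, about 7 to 11 of 300 were at risk at month 10.

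**The case against.** The study is declared cross-sectional and descriptive, and Table 16 says that the time is given in relapsers. Read literally, the number is correct for the group it names. Time since diagnosis is reported, and incident and prevalent patients are separated. All of that stands. But neither provision links relapse to a duration, and nothing in the table warns against reading the figure as time to relapse in the disease.

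A reader might infer that the reported time will be far too short, or that it will mainly measure how long ago the sample was diagnosed. The documents do not support either reading. The large shortfalls come from models that ignore the on-treatment criterion. Once it is modelled, the planned median is about 11, 20–21 and 27–29 months for true medians of 12, 24 and 36: it follows the true value and falls modestly below it. Nor do the documents show that durations differ between physician types. The point is that the planned table could not separate such a difference from a difference in relapse.

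It is also fair that Kaplan-Meier is no full cure. Censoring does not remove selection on treatment, and the all-patient curve can err by as much as the planned summary. That limits what should be asked of it.

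**Conclusion.** The point holds in this form: time to first relapse is right-truncated and biased short, and the relapse proportion has no time frame. In every scenario run the planned median was below the true one, with ratios from 0.24 to 0.92. The range depends on relapse rate, disease duration and treatment-course length, none of which the documents fix, and it assumes exponential relapse times. The direction was the same throughout; the size cannot be settled from the documents. The 6-week ceiling in the incident column needs no assumption.

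This is a secondary descriptive endpoint and the primary objective is unaffected. The change should still be made, because the table invites comparisons it cannot support and the remedy is cheap.

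**What to change.** In SAP 5.5.2 and Table 16:

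- Report the relapse proportion within classes of time since diagnosis (already derived in Appendix (3)), including within the comparisons by physician type.
- Add a Kaplan-Meier estimate of time from diagnosis to first relapse, censored at inclusion, with 95% CI and numbers at risk. The main figure is 6-month cumulative relapse in patients diagnosed at most 12 months before inclusion. Give no 12-month figure from that subset. Show the all-patient curve as supportive.
- If the relapsers-only time is kept, label it *among relapses observed before inclusion; not an estimate of time to relapse in GCA*, and drop it from the incident column.
- State as a limitation that entry requires being under treatment, which over-represents relapsers and which censoring does not remove.

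The cost is SAP wording and one extra SAS procedure on dates already collected. The drawbacks are a wider interval in the recent-diagnosis subset and some remaining selection bias.
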